6.2.1.2.1 Assessment of Severity

The severity, or intensity, of an AE refers to the extent to which an AE affects the participant's daily activities or their health. The intensity of the AE will be rated in accordance with the CTCAE version 5.0.

Changes in the severity of an AE should be documented to allow an assessment of the duration of the event at each level of intensity to be performed. Adverse events characterized as intermittent do not require documentation of onset and duration of each episode.

6.2.1.2.2 Assessment of Causality

The investigator's assessment of an AE's relationship to study drug is part of the documentation process. Regardless of the investigator's assessment of an AE's relationship to study drug, the AE must be reported.

The relationship or association of the study drug in causing or contributing to the AE will be characterized using the following classification and criteria:

Unrelated: There is no association between the study drug and the reported event.

Possible: Treatment with the study drug caused or contributed to the AE, ie, the event follows a reasonable temporal sequence from the time of drug administration or follows a known response pattern to the study drug but could also have been produced by other factors.

Probable: A reasonable temporal sequence of the event with drug administration exists and, based upon the known pharmacological action of the drug, known or previously reported adverse reactions to the drug or class of drugs, or judgment based on the investigator's clinical experience, the association of the event with the study drug seems likely. The event disappears or decreases on cessation or reduction of the dose of study drug.

Definite: A definite causal relationship exists between drug administration and the AE, and other conditions (concurrent illness, progression/expression of disease state, or concurrent medication reaction) do not appear to explain the event. The event reappears or worsens if the study drug is re-administered.

6.2.1.3 Reporting Adverse Events

All AEs reported or observed during the study will be recorded on the AE page in the eCRF.

Information to be collected includes the following:

- Dose (number of capsules per day)
- Description of the event / event term
- Date and time of onset
- Investigator-specified assessment of severity

- Investigator-specified assessment of causal relationship to study drug
- Date and time of resolution of the event
- Seriousness
- Lot/batch number
- Any required treatment or evaluations
- Action taken with the study drug due to the event
- Outcome
- Investigator-specific assessment if the AE is related to a recent/current COVID infection
- If a COVID positive PCR test received within last 14 days

Adverse events resulting from concurrent illnesses, reactions to concurrent illnesses, reactions to concurrent medications, or progression of disease states must also be reported. All AEs will be followed to adequate resolution. The then-current version of MedDRA will be used to code all AEs.

Any medical condition that is present at the time that the participant is screened but does not deteriorate should not be reported as an AE, but it should be captured in the medical history page(s) of the eCRF. However, it should be recorded as an AE at any time during the study that it deteriorates to a greater extent than would be expected.

If there is any doubt as to whether a clinical observation is an AE, the event should be reported.

6.2.1.3.1 Reporting Serious Adverse Events

Any AE that meets SAE criteria (Section 6.2.1.1) must be reported to [REDACTED] [REDACTED] immediately (ie, within 24 hours) after the time site personnel first learn about the event.

To report the SAE, the investigator must record the SAE on the AE eCRF in the EDC system as well as any relevant eCRF forms (eg, drug dispensation eCRF, applicable laboratory eCRF). When the AE eCRF is completed, [REDACTED] personnel will be notified electronically automatically and will retrieve the form. If the event meets serious criteria and it is not possible to access the EDC system, please complete the back-up paper SAE Form and send it by e-mail to [REDACTED] Safety at [REDACTED], or call the [REDACTED] SAE hotline and fax the completed paper SAE Form to [REDACTED] within 24 hours of awareness. When the EDC system becomes available, the SAE information must be entered within 24 hours of the system becoming available.

Safety Contact Information: [REDACTED]

[REDACTED]	[REDACTED]	[REDACTED]

The sponsor has a legal responsibility to notify both the local regulatory authority and other regulatory agencies about the safety of a study drug under clinical investigation. The sponsor will comply with country-specific regulatory requirements relating to safety reporting to the regulatory authority, IRB/IEC, and investigators.

An investigator who receives a safety notification letter describing a SUSAR or other specific safety information from the sponsor will review and then file it as appropriate and will notify the local IRB/IEC, if appropriate according to local requirements.

6.2.1.3.2 Reporting Suspected Unexpected Serious Adverse Reactions

The sponsor will promptly evaluate all SUSARs against cumulative product experience to identify and expeditiously communicate possible new safety findings to investigators, IRBs/IECs, and applicable health authorities based on applicable legislation.

To determine reporting requirements for single SAE cases, the sponsor will assess the expectedness of these events using the approved version of the EDP1815 IB at the time of

event onset, comparing the severity of each SUSAR and the cumulative event frequency reported for the study with the severity and frequency reported in the EDP1815 IB.

Reporting requirements will also be based on the investigator's assessment of causality and seriousness, with allowance for upgrading by the sponsor as needed. If an AE, after causality and expectedness assessment, is regarded as a potential SUSAR by the medical monitor and in agreement with the sponsor, unblinding for regulatory reporting purposes must be performed before notification of the SUSAR to the regulatory authorities and IRBs/ECs, as applicable. The procedure must ensure that the identity of the IMP is only revealed to those that need to obtain this information.

6.2.1.4 Follow-Up of Participants Reporting Adverse Events

All AEs must be reported in detail on the appropriate page in the eCRF and followed to satisfactory resolution, until the investigator deems the event to be chronic or not clinically significant, the event is considered stable, the participant dies, or the participant is lost to follow-up.

6.2.2 Bristol Stool Form Scale

The BSFS is a classification system for the form (appearance) of human feces (O'Donnell et al 1990) that has been determined to be a reliable and validated assessment that correlates well with stool water content (Blake et al 2016). In addition, the *Prevotella* enterotype has been found to be more abundant in subjects with looser stools (Vandeputte et al 2016).

The BSFS classifies human feces into 7 consistency categories, with the highest scores corresponding to loose stools and fast colon transit and the lowest scores corresponding to hard stools (low stool water content) and slow colon transit.

During the screening period, participants will complete a 7-day stool diary over the week before the baseline visit. Participants will record in the diary the date and time of each defecation, as well as its BSFS category. Participants will bring their completed diaries to the baseline visit, when study staff will collect it for entry in the eCRF.

6.2.3 Physical Examinations

A complete physical examination will be conducted, including assessments of the skin and cardiovascular, respiratory, GI, and neurological systems. Height (at screening only) and

weight will also be measured and recorded (without shoes, street clothing). Body mass index will be calculated from the height and weight. Investigators should pay special attention to clinical signs related to previous serious illnesses.

6.2.4 Vital Signs

Blood pressure, pulse rate, respiratory rate, and temperature will be assessed. Blood pressure and pulse measurements will be assessed in a sitting position with a completely automated device. Blood pressure and pulse measurements should be preceded by at least 5 minutes of rest for the participant in a quiet setting without distractions (eg, television, mobile phones).

Vital signs (to be checked prior to any procedures) will consist of 1 pulse rate and 3 blood pressure measurements (3 consecutive blood pressure readings will be recorded at intervals of at least 1 minute). The lowest of the 3 blood pressure readings will be recorded on the eCRF.

6.2.5 Electrocardiograms

Single 12-lead ECGs will be obtained as outlined in the SoA (Table 6-1) using an ECG machine that automatically calculates the heart rate and measures PR, RR, QRS, QT, and QTcF intervals.

At each visit, a single individual ECG tracing should be obtained: if, in the judgment of the investigator, the ECG tracing appears to be clinically significant, it should be repeated. If the repeated tracing also appears clinically significant, the investigator should report the abnormality as an AE and consult with the medical monitor to decide whether the participant should continue treatment in the study.

6.3 Pregnancy

Pregnancy is not regarded as an AE unless there is a suspicion that a study drug may have interfered with the effectiveness of a contraceptive medication. Any pregnancy that occurs during study participation or up to 28 days after the final dose of study drug must be reported to [REDACTED] Safety by phone or email, within 2 weeks of learning of its occurrence.

[REDACTED] Safety will send the Exposure in Utero Form to the site for completion within 24 hours. This form should be completed and returned to [REDACTED] Safety within 24 hours of receipt. The pregnancy must be followed up until the first “well-baby

visit" (or similarly purposed visit 6 to 8 weeks postpartum) to determine outcome (including spontaneous miscarriage, elective termination, normal birth, or congenital abnormality) and status of mother and child, even if the participant was discontinued from the study. If the outcome of the pregnancy meets the criteria for immediate classification as an SAE (ie, postpartum complication, spontaneous abortion, stillbirth, neonatal death, congenital anomaly, ectopic pregnancy), the investigator should follow the procedures for reporting an SAE. Pregnancy complications and elective terminations for medical reasons must be reported as an AE or SAE. Spontaneous miscarriages must be reported as an SAE.

Any SAE occurring in association with a pregnancy, brought to the investigator's attention after the participant has completed the study, and considered by the investigator as possibly related to the study treatment, must be promptly reported to [REDACTED].

6.4 Laboratory Analyses

Any abnormal laboratory test results (hematology, clinical chemistry, or urinalysis) or other safety assessments (eg, ECGs, vital sign measurements), including those that worsen from baseline or are clinically significant in the medical and scientific judgment of the investigator, are to be recorded as AEs or SAEs. However, any clinically significant safety assessments that are associated with the underlying disease, unless judged by the investigator to be more severe than expected for the participant's condition, are **not** to be reported as AEs or SAEs.

Standard laboratory analyses to understand safety and tolerability include the following:

- Blood or plasma analytes: urea, creatinine, sodium, potassium, ALT, AST, total and direct bilirubin, CRP, creatine kinase, fasting glucose, fasting lipid panel (total cholesterol, HDL, LDL, triglycerides)
- Hematologic analyses: full blood count, including hemoglobin, MCV, MCH, MCHC, hematocrit, percent reticulocytes, platelet count; differential white blood cell count including neutrophils, lymphocytes, monocytes, and eosinophils
- Urinalysis by dip stick: protein, blood, glucose, ketones, bilirubin, pH, nitrites, and specific gravity

Other screening tests include the following:

- Serology (HIV antibody, HbsAg, and HCV antibody)
- Serum pregnancy test (HCG) at screening, urine test thereafter

Blood samples for assessment of fasting blood glucose and lipid panel will be obtained after the participant has fasted for at least 8 hours.

A central laboratory (or specialized central laboratories) will be used for all laboratory analyses. Details of sample collection and handling procedures will be provided in the specific laboratory manual.

The investigator must review the laboratory reports, document this review, and record any clinically relevant changes occurring during the study. If the laboratory reports are not transferred electronically, the values must be filed with the source information (including reference ranges). In most cases, clinically significant abnormal laboratory findings are those that are not associated with the underlying disease, unless judged by the investigator to be more severe than expected for the participant's condition.

All laboratory tests with values considered clinically significantly abnormal during participation in the study or within 30 days after the last dose of study drug should be repeated until the values return to normal or baseline or are no longer considered clinically significant by the investigator or medical monitor. If such values do not return to normal/baseline within a time judged reasonable by the investigator, the etiology should be identified, and the sponsor notified.

All protocol-required laboratory assessments, as defined in this section, must be conducted in accordance with the laboratory manual and the SoA (Table 6-1). Screening laboratory results will be used to confirm eligibility at Visit 2 (Baseline). If laboratory values from non-protocol-specified laboratory assessments performed at the institution's local laboratory require a change in participant management or are considered clinically significant by the investigator (eg, SAE or AE or dose modification), then the results must be recorded in the eCRF.

6.4.1 Blood Volume

The planned maximum amount of blood collected from each participant over the duration of the study, including any extra assessments that may be required, will not exceed 130 mL. Repeat or unscheduled samples may be taken for safety reasons or for technical issues with the samples. The planned maximum amount of blood collected from each participant at a single visit will not exceed 46 mL, and the planned maximum amount of blood collected from each participant over 30 days will not exceed 58 mL.

6.4.2 Pharmacokinetics

Systemic exposure following oral EDP1815 dosing is estimated to be very low based on lack of detection in blood (<0.01% of administered dose). However, plasma samples will be taken from all participants for the estimate of systemic EDP1815 levels by PCR with strain-specific primers that can detect EDP1815 specifically, even when other strains of *Prevotella histicola* are present. Any effects of EDP1815 on the gut microbiome will be investigated using 16S ribosomal RNA sequencing, which measures both the presence and quantity of microbes at the genus level. Sampling will be performed as specified in the SoA (Table 6-1, blood sample for systemic levels of microbes).

6.4.3 Pharmacodynamics and Biomarkers

Procedures for sample collection, processing, storage, and shipment will be detailed in the study specific laboratory manual. Biomarkers are exploratory endpoints and analytical results for biomarkers will not be included in the CSR. They will be reported separately from the CSR.

Digital photographs should be taken of up to 6 lesion sites that have a lesion area ideally greater than 2 cm by 2 cm at baseline. The same locations photographed at baseline should be followed throughout the study for each participant. Procedural details for digital photography will be provided in the specific user manual.

6.4.3.1 Histologic Assessment

A 4 mm punch biopsy will be taken by suitably trained study personnel (see Section 6.1.10). Standard histology will be performed on skin plaque biopsies (including epidermal thickness, basal mitotic counts and immune cell infiltrates, immunohistochemistry) from approximately

15 participants in each cohort. Details will be provided in the study specific laboratory manual. The histologic evaluations are exploratory and are outside the scope of the CSR.

6.4.3.2 mRNA Transcription Analysis

An mRNA transcription analysis will be performed on the skin plaque biopsies.

6.4.3.3 Blood Cytokine and Chemokine Analysis

Blood samples will be stimulated ex vivo and analyzed for levels of cytokines and chemokines, including IL-1 beta, IL-2, IL-4, IL-6, IL-8, IL-10, IL-12p40, IL-17A, TNF α , and IFN γ (ie, exploratory biomarkers).

6.4.3.4 Analysis of Fecal Microbiome

The microbiome composition of stool samples will be assessed by 16S ribosomal RNA sequencing, which looks at the diversity and abundance of microbes in the colonic microbiome (Human Microbiome Project Consortium 2012). EDP1815 is not expected to alter the composition of the microbiome, but it is being evaluated as a safety biomarker.

7 Statistical Considerations

Analysis methods for key endpoints are described below. Further details on all analyses will be described in the SAP.

No formal hypothesis will be tested. A model-based probability inference approach in a Bayesian framework will be used to guide decision-making around dose selection. Posterior estimates and 95% CrI for the difference between each active dose and placebo will be produced for relevant primary and secondary endpoints.

Unless otherwise specified, missing data will be considered as missing at random and will be accounted for using mixed models for repeated measures, with all time points collected for the relevant endpoint included in the model. This includes data which is excluded due to collection after treatment discontinuation or after a protocol deviation as applicable to the definition of the estimands used in the analysis.

The primary analysis for the study will occur after all participants have completed 4 weeks of follow-up after their last dose of study medication (end of Part A). The final analysis for the study will occur when all participants have completed the required relapse and rebound follow-up period of up to 24 weeks post-treatment (end of Part B).

7.1 Estimands and Intercurrent Events

7.1.1 Primary Efficacy Estimand

The primary estimand will be the effect of EDP1815 on the percent change in PASI score from baseline to Week 16 in the mITT set of all treated participants, regardless of deviations from the protocol. Only data collected while on treatment will be used to account for the intercurrent event of treatment discontinuation (hypothetical strategy based on adherence to treatment only). The posterior mean difference between each active dose and the pooled placebo will be estimated.

Percent change from baseline in PASI score at each visit will be calculated as:

$$100 * (\text{PASI score at Visit} - \text{baseline PASI score}) / \text{baseline PASI score}.$$

A negative percentage change from baseline will indicate an improvement.

For the primary analysis, 3 supportive estimands will also be considered:

- To assess the impact of intercurrent events related to protocol deviations believed to impact efficacy, a supportive analysis will be performed where all data collected after any such identified protocol deviations will be excluded. Participants who had a protocol deviation believed to impact efficacy prior to the first dose of treatment (hypothetical strategy based on adherence to treatment and the aspects of the protocol which impact efficacy) will be completely excluded from this analysis.
- To assess the impact of treatment discontinuation for any reason, a supportive analysis will be performed in which all data collected up to the end of Week 16, including any data collected after treatment discontinuation will be included (treatment policy strategy).
- To assess the impact of treatment discontinuation due to a requirement for alternative therapy, a supportive analysis will be performed where the highest PASI score recorded prior to treatment discontinuation will be applied to all expected visits after treatment discontinuation up to Week 16.

The primary analysis will be performed using a Bayesian MMRM as fully described in Section 7.6.1. Data from visits prior to Week 16 will be included in the model and missing data will not be explicitly imputed.

Supportive analyses will also be performed in the same manner, using the 3 supportive estimands as defined above. These will explore the possible impact of the intercurrent events of treatment discontinuation for any reason, treatment discontinuation due to requirement for alternative treatment, and events relating to protocol deviations that may have an impact on efficacy.

7.1.2 Secondary Efficacy Estimands

Estimands for the analyses of all secondary endpoints are shown in Table 7-1.

Table 7-1 **Summary of Secondary Estimands**

Population of interest	Endpoint	Consideration of intercurrent events	Summary measure
mITT set	Mean percentage change from baseline in PASI Score at Weeks 4, 8, and 12	To include all data collected prior to treatment discontinuation, regardless of protocol deviations	Posterior mean difference between each active treatment group and pooled placebo at each visit
mITT set	Mean absolute change from baseline in PASI Score at Weeks 4, 8, 12, and 16	To include all data collected prior to treatment discontinuation, regardless of protocol deviations	Posterior mean difference between each active treatment group and pooled placebo at each visit
mITT set	Achievement of PASI-50 at Weeks 4, 8, 12, and 16	To include all data collected prior to treatment discontinuation, regardless of protocol deviations	Posterior odds ratio for response between each active treatment group and pooled placebo at each visit
mITT set	Time to first achievement of PASI-50	To include all data collected prior to treatment discontinuation, regardless of protocol deviations	Hazard ratio for each active group versus placebo
mITT set	Achievement of PASI-75, PASI-90 and PASI-100 at Week 16	To include all data collected prior to treatment discontinuation, regardless of protocol deviations	Proportion of response for each endpoint in each treatment group at each visit
mITT set	Achievement of PGA of 0 or 1 with a ≥ 2 -point improvement from baseline at Week 16	To include all data collected prior to treatment discontinuation, regardless of protocol deviations	Posterior odds ratio for response between each active treatment group and pooled placebo
mITT set	Achievement of PGA of 0 at Week 16	To include all data collected prior to treatment discontinuation, regardless of protocol deviations	Posterior odds ratio for response between each active treatment group and pooled placebo
mITT set	Mean percentage change from baseline in PGA \times BSA at Weeks 4, 8, 12, and 16	To include all data collected prior to treatment discontinuation, regardless of protocol deviations	Posterior mean difference between each active treatment group and pooled placebo at each visit
mITT set	Mean absolute change from baseline in PGA \times BSA at Weeks 4, 8, 12, and 16	To include all data collected prior to treatment discontinuation, regardless of protocol deviations	Posterior mean difference between each active treatment group and pooled placebo at each visit
mITT set	Mean percentage change from baseline in LSS at Weeks 4, 8, 12, and 16	To include all data collected prior to treatment discontinuation, regardless of protocol deviations	Posterior mean difference between each active dose and pooled placebo at each visit
mITT set	Mean absolute change from baseline in LSS at Weeks 4, 8, 12, and 16	To include all data collected prior to treatment discontinuation, regardless of protocol deviations	Posterior mean difference between each active dose and pooled placebo at each visit
mITT set	Mean percentage change from baseline in DLQI score at Weeks 4, 8, 12, and 16	To include all data collected prior to treatment	Posterior mean difference between each active dose and pooled placebo at each visit

Population of interest	Endpoint	Consideration of intercurrent events	Summary measure
		discontinuation, regardless of protocol deviations	
mITT set	Mean absolute change from baseline in DLQI score at Weeks 4, 8, 12, and 16	To include all data collected prior to treatment discontinuation, regardless of protocol deviations	Posterior mean difference between each active dose and pooled placebo at each visit
mITT set	Mean percentage change from baseline in mNAPSI total score at Weeks 4, 8, 12, and 16	To include all data collected prior to treatment discontinuation, regardless of protocol deviations	Posterior mean difference between each active dose and pooled placebo at each visit
mITT set	Mean absolute change from baseline in mNAPSI total score at Weeks 4, 8, 12, and 16	To include all data collected prior to treatment discontinuation, regardless of protocol deviations	Posterior mean difference between each active dose and pooled placebo at each visit
Week 16 responders set	Cumulative incidence of partial relapse at Weeks 20, 24, 28, and 40	To include all data collected after treatment discontinuation	Proportion of participants to relapse in each treatment group at each visit
Week 16 responders set	Cumulative incidence of complete relapse at Weeks 20, 24, 28, and 40	To include all data collected after treatment discontinuation	Proportion of participants to relapse in each treatment group at each visit
mITT set	Cumulative incidence of rebound at Weeks 20, 24, 28, and 40	To include all data collected after treatment discontinuation	Proportion of participants to rebound in each treatment group at each visit

Summaries and analyses of the secondary endpoints are detailed in full in Section 7.6.2.

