For the PASI-50, a generalized linear mixed effects model with a logit link function will be fitted using data from all visits. Treatment, visit, and baseline PASI score terms will be included in the model as fixed effects, together with treatment*visit and baseline PASI score*visit interactions, and any baseline covariates selected in the primary analysis model for the primary estimand. Odds ratios and 95% CIs for each active dose compared to placebo at each visit will be presented.

A supportive analysis for the PASI-50 will also be performed, in the same manner as described above, in which participants who withdraw from study drug before Week 16 due to requirement for alternative therapy will be included in the model with the PASI-50 endpoint imputed as ‘not achieved’ at all expected visits after study drug withdrawal.

A sensitivity analysis will also be performed on the PASI-50. Bayesian logistic regression models will be individually fitted at each of Weeks 4, 8, 12, and 16. The model will include parameters for treatment and baseline PASI score together with any baseline covariates selected in the primary analysis model for the primary estimand. The posterior odds-ratios for each pairwise comparison of an active EDP1815 dose and placebo with associated 95% HDP CrI will be presented together with the posterior probability that the true odds ratio >1.

Percentage of participants achieving PGA of 0 or 1 with a ≥ 2 -point improvement and percentage of participants achieving a PGA of 0 will be analyzed in the same manner as described above for PASI-50 with the exception that the sensitivity analysis using the Bayesian logistic regression model will only be fitted on the Week 16 data.

For the time to first achievement of PASI-50, a nonparametric survival analysis for interval censored data will be performed. The expectation-maximization iterative complex minorant (EMICM) method for iterative computation of the nonparametric maximum likelihood

estimator for the survival function (Wellner and Zahn 1997) will be used. The number and proportion of participants who meet the PASI-50 at least once during the study will be presented. A generalized log-rank test will be used to compare each active dose with placebo and the p-value for treatment difference will also be presented. The estimated survival curves for each treatment group will also be presented.

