9.5.5 Time to First Achievement of PASI-50

The time to first achievement of the PASI-50 will be analysed using a nonparametric survival analysis for interval-censored data. The expectation-maximisation iterative complex minorant (EMICM) method for iterative computation of the nonparametric maximum likelihood estimator for the survival function ([Wellner and Zhan 1997](#)) will be used.

Treatment will consist of 4 levels or 6 levels based on the appropriateness of the placebo pooling strategy as per the main analytical approach for the primary analysis.

The number and proportion of participants who meet the PASI-50 at least once during the study will be presented. Where calculable, the time to 25% and 50% of participants with PASI-50 will be displayed with its 95% confidence interval. A generalised log-rank test will be used to compare each active dose with placebo and the p-value for treatment difference will also be presented.

A figure showing the estimated survival curves of each treatment group will also be presented.

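### Time to first PASI-50: the protocol declares a hazard ratio as the summary measure, but no planned analysis estimates it, and the only between-group result is a descriptive log-rank p-value

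*Protocol*

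**What the plan says.** **The declared measure.** Protocol 7.1.2, Table 7-1, has a row for time to first achievement of PASI-50 in the mITT set, using data collected before treatment discontinuation. Its summary measure is "Hazard ratio for each active group versus placebo". The synopsis table of secondary estimands says the same. Protocol 7.1.2 then points to the analysis section: "Summaries and analyses of the secondary endpoints are detailed in full in Section 7.6.2".

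**The planned analysis.** For this endpoint Protocol 7.6.2 specifies "a nonparametric survival analysis for interval" censored data, with the EMICM algorithm for the nonparametric maximum likelihood estimate (NPMLE) of the survival function. It adds the number and proportion of participants reaching PASI-50, and then: "A generalized log-rank test will be used to compare each active dose with placebo and the p-value for treatment difference will also be presented". Last come the curves: "The estimated survival curves for each treatment group will also be presented".

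SAP 9.5.5 follows the same route: "The time to first achievement of the PASI-50 will be analysed using a nonparametric survival analysis for interval-censored data". It repeats the counts ("The number and proportion of participants who meet the PASI-50 at least once during the study will be presented") and the test ("A generalised log-rank test will be used to compare each active dose with placebo and the p-value"). It adds the time by which 25% and 50% of participants have reached PASI-50, with 95% confidence intervals, where these can be calculated. The introduction to SAP Section 9 adds Kaplan-Meier summaries for time-to-event endpoints.

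**The outputs.** SAP Section 15.2 lists one table (14.2.4) and one survival-curve figure (14.2.4) for this endpoint. Neither title mentions a hazard ratio.

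**The concern.** The summary measure tells the reader what number will express the treatment effect. Here that number is a hazard ratio, and someone following both documents to the letter would never calculate one. The NPMLE describes each arm separately, and the log-rank test gives a p-value but no magnitude.

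At stake is whether the report can say how much sooner, or how much more often over time, participants on a given dose reach PASI-50 than those on placebo. The study is meant to inform dose selection, and time to onset of response is one of its exploratory objectives. Three p-values do not let a reader compare the doses on speed of response. There is also a reporting risk: if the mismatch is noticed only after unblinding, the choice of an effect measure for this endpoint becomes a post hoc decision.

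**Working it through.** The documents give no figure for this endpoint that could be reproduced, so the main check sets the passages side by side.

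**Step 1. Could any planned output be the declared measure?**

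| Planned output | Source | Compares arms? | Hazard ratio? |
|---|---|---|---|
| NPMLE survival curves | Protocol 7.6.2, SAP 9.5.5 | No, per arm | No |
| Number and proportion reaching PASI-50 | Protocol 7.6.2, SAP 9.5.5 | No, per arm | No |
| Times to 25% and 50%, 95% CI | SAP 9.5.5 | No, per arm | No |
| Kaplan-Meier summaries | SAP Section 9 | No, per arm | No |
| Generalized log-rank p-value | Protocol 7.6.2, SAP 9.5.5 | Yes | No |

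No row yields a hazard ratio, and only the last compares arms.

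**Step 2. Does the SAP replace the measure?** SAP 4.2 lists the endpoint without a summary measure. SAP 9.5 carries the primary estimand approach over to the secondary endpoints, but the measure in SAP 9.4.1 is a difference in mean percentage change, which has no meaning for a time to event. SAP 9.5.3.1 names the odds ratio, but only for the response endpoints. SAP Table 8 lists four changes from the protocol (interim timing, DLQI sensitivity analyses, definition of partial relapse, Part B population), and none concerns this endpoint. The protocol's hazard ratio therefore stands.

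**Step 3. Is the mismatch only with superseded text?** No. The Amendment 4 summary explains the cause, since it records that a Bayesian Cox model was replaced by the nonparametric method. But the conflict is between the current Table 7-1 and synopsis on one side and the current Protocol 7.6.2 and SAP 9.5.5 on the other.

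**Step 4. Do other rows of Table 7-1 have the same gap?** Mean differences come from the MMRM, posterior odds ratios from the Bayesian logistic sensitivity analyses, and proportions from the tabulations. The hazard-ratio row is the one with no matching estimate.

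**Step 5. Can a reader recover the effect from the p-value?** Not from the p-value alone. As an illustration, take 50 active against 75 pooled placebo participants, so the allocation fractions are 50/125 = 0.4 and 75/125 = 0.6. With E participants reaching PASI-50 across the two arms, the usual approximation is SE(log HR) = 1/√(E × 0.4 × 0.6), and a two-sided p of 0.05 in favour of active corresponds to HR = exp(1.96 × SE). The documents give no value for E, so 20 to 60 is an assumption.

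- E = 20: SE = 1/√4.8 = 0.456, HR about 2.45
- E = 40: SE = 1/√9.6 = 0.323, HR about 1.88
- E = 60: SE = 1/√14.4 = 0.264, HR about 1.68

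The same p-value fits quite different effects. The formula is for ordinary right-censored data, so with interval censoring these values are only indicative.

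**The case against.** The strongest reply is that this is a table cell left behind by an amendment and not a faulty analysis. Amendment 4 moved deliberately to a method that suits visit-based data and avoids a proportional-hazards assumption, and the SAP's analysis and output list agree with each other. The neighbouring PASI-50 and PGA rows still refer to posterior odds ratios although their main analysis is now a frequentist mixed model. This explanation is probably right, and it bears on the remedy: nothing shows the nonparametric method to be wrong, and a hazard model should not be forced back in. It does not close the gap, because correcting the cell alone would still leave the endpoint without a between-group estimate.

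The practical loss is also limited. Odds ratios for PASI-50 with 95% intervals, adjusted for baseline PASI, are planned at Weeks 4, 8, 12 and 16 (Protocol 7.6.2, SAP 9.5.3). They do not measure time to first response, but the onset pattern is not left without effect estimates. This stands and keeps the severity low.

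A reader might infer three stronger points that the documents do not support:

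- **That the endpoint is reported without any estimate or interval.** Per-arm proportions are planned, as are times to 25% and 50% with confidence intervals. What is missing is a between-group estimate.
- **That a promised baseline PASI adjustment has been omitted.** For this endpoint it appears only in the amendment history. The current covariate rule covers models that include covariates, and the NPMLE with a log-rank test has none.
- **That a p-value here contradicts the plan's emphasis on estimation.** That emphasis is given as the reason for not adjusting for multiplicity, and Protocol 7.6.2 allows p-values for secondary endpoints and labels them descriptive.

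**Conclusion.** The inconsistency is real and lies wholly in current text. Followed exactly, the plan produces the declared summary measure for none of the three dose-placebo comparisons, and no between-group time-to-event effect with an interval for this endpoint. The hazard ratio is unplanned but not out of reach, since the interval data would support estimating one.

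Severity is minor. The endpoint is secondary, its results are descriptive without multiplicity control, and the primary analysis and sample size do not depend on it. The conclusion rests on reading the documents and not on the assumed event counts, which only illustrate why a p-value cannot stand in for an effect size.

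**What to change.** Align the estimand and the analysis before unblinding, by one of two routes.

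**(a) Keep the nonparametric method and change the measure.** In Table 7-1 and the synopsis, restate the summary measure as the difference between each active dose and placebo in the NPMLE probability of having reached PASI-50 by Week 16. Add that difference with a 95% confidence interval to SAP 9.5.5 and Table 14.2.4. State the day on which the curve is read and how the interval is obtained (for example by bootstrap within arm), because the NPMLE does not fix the curve's shape inside an interval. This keeps the choice made in Amendment 4 and adds no hazard assumption.

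**(b) Keep the hazard ratio and add a model for it.** Add an interval-censored proportional hazards model to Protocol 7.6.2 and SAP 9.5.5, reporting the hazard ratio with a 95% interval for each dose beside the NPMLE curves. The price is a proportional-hazards assumption that the present plan avoids.

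Under either route the comparator should follow the placebo pooling decision, and any departure from the protocol text should be recorded in SAP Table 8. The cost is one additional estimate per dose. SAP 5.3.3.3 already derives the interval start and end days, so no new data are needed.
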